#### Notification of Investigators

The sponsor must notify all participating investigators (i.e., all investigators to whom the sponsor is providing drug under its INDs or under any investigator’s IND) in an IND safety report of potential serious risks, from clinical trials or any other source, as soon as possible, but in no case later than 15 calendar days after the sponsor determines that the information qualifies for reporting.

#### Process

If the sponsor deems that an event is both a serious SAR AND unexpected, it must also (in addition to Oncore) be recorded on the MedWatch Form 3500A as per 21 CFR 312.32. Unexpected adverse events or adverse reaction refers to an event or reaction that is not listed in the investigator’s brochure or is not listed at the specificity or severity that has been observed; or if an investigator’s brochure is not required or available, is not consistent with the risk information described in the general investigation plan or elsewhere in the current IND application.

The MedWatch form and supporting documents defining the event and causality should be faxed to the Multicenter Project Manager at [contact] (or emailed, with address provided at the Start up Meeting (SIM)) along with supporting documentation defining the event and causality. The Multicenter Project Manager will then send the report to the Funding Source and notify the Multicenter and CPO Regulatory Associate of the event.

The MedWatch 3500a form can be accessed at:

<http://www.fda.gov/Safety/MedWatch/HowToReport/DownloadForms/default.htm>.

(Please be sure and access form 3500a, and not form 3500).

Once the UNC Principal Investigator determines an event is a serious SAR AND unexpected, the MedWatch 3500A form will be submitted to the FDA. If the event is serious, unexpected and considered to be possibly-, probably- or definitely-related to the study treatment, the Multicenter Project Manager will inform the Regulatory Associate at UNC and IND Specialist. The MedWatch form will be submitted according to LCCC SOP for safety reporting for a multi-site study.

All IND safety reports must be submitted on Form 3500A and be accompanied by Form 1571. The FDA must be notified of any unexpected or life-threatening suspected adverse reactions as soon as possible, but no later than 7 calendar days of learning of the event.

The Multicenter Project Manager will also be responsible for informing each Affiliate site of all serious and unexpected SARs reported to the FDA via fax as soon as possible.

#### Additional Reporting Requirements

The following additional items must be reported via IND safety report:

- *Findings from other studies.* The sponsor must report any findings from epidemiological studies, pooled analysis of multiple studies, or clinical studies, whether or not conducted under an IND, and whether or not conducted by the sponsor, that suggest a significant risk to humans exposed to the drug.
- *Findings from animal or in vitro testing.* The sponsor must report any findings from animal or *in vitro* testing, whether or not conducted by the sponsor, that suggest a significant risk in humans exposed to the drug, such as reports of mutagenicity, teratogenicity, or carcinogenicity, or reports of significant organ toxicity t or near the expected human exposure.
- *Increased rate of occurrence of serious suspected adverse reactions.*

#### Additional Guidance

Please refer to 21CFR312.32 and “Guidance for Industry and Investigators: Safety Reporting Requirements for INDs and BA/BE Studies” for additional information

and reporting requirements. All IND Safety Reports will be submitted in accordance with these regulations/guidances.

### 7.3.3.1 Merck Reporting Requirements:

For the time period beginning when the consent form is signed until treatment allocation/randomization, any serious adverse event, or follow up to a serious adverse event, including death due to any cause other than progression of the cancer under study that occurs to any subject must be reported within 24 hours to the Sponsor and within 2 working days to Merck Global Safety if it causes the subject to be excluded from the trial, or is the result of a protocol-specified intervention, including but not limited to washout or discontinuation of usual therapy, diet, placebo treatment or a procedure.

For the time period beginning at treatment allocation/randomization through 90 days following cessation of treatment, or 30 days following cessation of treatment if the subject initiates new anticancer therapy, whichever is earlier, any serious adverse event, or follow up to a serious adverse event, including death due to any cause other than progression of the cancer under study whether or not related to the Merck product, must be reported within 24 hours to the Sponsor and within 2 working days to Merck Global Safety.

Additionally, any serious adverse event, considered by an investigator who is a qualified physician to be related to Merck product that is brought to the attention of the investigator at any time following consent through the end of the specified safety follow-up period specified in the paragraph above, or at any time outside of the time period specified in the previous paragraph also must be reported immediately to the Sponsor and to Merck Global Safety.

All subjects with serious adverse events must be followed up for outcome.

**SAE reports and any other relevant safety information are to be forwarded to the Merck Global Safety [contact]**

All 15-Day Reports and Annual Progress Reports must be submitted as required to FDA. Investigators will cross-reference these reports to the Merck Investigational Compound Number (IND, CSA, etc.) at the time of submission. Additionally investigators will submit a copy of these reports to Merck & Co., Inc. (Attn: Worldwide Product Safety; [contact]) at the time of submission to FDA.

#### **Events of Clinical Interest**

Selected non-serious and serious adverse events are also known as Events of Clinical Interest (ECI) and must be recorded as such on the Adverse Event case report forms/worksheets and reported within 24 hours to the Sponsor and within 2 working days to Merck Global Safety. (Attn: Worldwide Product Safety; [contact])

For the time period beginning when the consent form is signed until treatment allocation, any ECI, or follow up to an ECI, that occurs to any subject must be reported within 24 hours to the Sponsor and within 2 working days to Merck Global Safety if it causes the subject to be excluded from the trial, or is the result of a protocol-specified intervention, including but not limited to washout or discontinuation of usual therapy, diet, placebo treatment or a procedure.

For the time period beginning at treatment allocation/randomization through 90 days following cessation of treatment, or 30 days following cessation of treatment if the subject initiates new anticancer therapy, whichever is earlier, any ECI, or follow up to an ECI, whether or not related to Merck product, must be reported within 24 hours to the Sponsor and within 24 hours to Merck Global Safety.

Events of clinical interest for this trial include:

1. An overdose of Merck product, as defined in section 5.1.10
2. An elevated AST or ALT lab value that is greater than or equal to 3X the upper limit of normal and an elevated total bilirubin lab value that is greater than or equal to 2X the upper limit of normal and, at the same time, an alkaline phosphatase lab value that is less than 2X the upper limit of normal, as determined by way of protocol-specified laboratory testing or unscheduled laboratory testing.

\* Note: These criteria are based upon available regulatory guidance documents. The purpose of the criteria is to specify a threshold of abnormal hepatic tests that may require an additional evaluation for an underlying etiology. Asymptomatic Gilbert's disease will be an allowed exception.

Pregnancy and Lactation

See above in this section for additional information. Such events must be reported within 2 working days to Merck Global Safety. (Attn: Worldwide Product Safety; [contact]).

Protocol-Specific Exceptions to Serious Adverse Event Reporting

Efficacy endpoints as outlined in this section will not be reported to Merck as unless there is evidence suggesting a causal relationship between the drug and the event. Any such event will be submitted to the Sponsor within 24 hours and to Merck Global Safety within 2 working days either by electronic or paper media. Specifically, the suspected/actual events covered in this exception include any event that is disease progression of the cancer under study.

The Sponsor will monitor efficacy endpoint events and safety data to ensure the safety of the subjects in the trial. Any suspected endpoint which upon review is not progression of the cancer under study will be forwarded to Merck Global Safety as a SAE within 2 working days of determination that the event is not progression of the cancer under study

Hospitalization related to convenience (e.g. transportation issues etc.) will not be considered a SAE.

#### **7.4 Data and Safety Monitoring Plan**

The Principal Investigator will provide continuous monitoring of patient safety in this trial with periodic reporting to the Data and Safety Monitoring Committee (DSMC).

Meetings/teleconferences will be held at a frequency dependent on study accrual, and in consultation with the study Biostatistician. These meetings will include the investigators as well as protocol nurses, clinical research associates, regulatory associates, data managers, biostatisticians, and any other relevant personnel the principal investigators may deem appropriate. At these meetings, the research team will discuss all issues relevant to study progress, including enrollment, safety, regulatory, data collection, etc.

The team will produce summaries or minutes of these meetings. These summaries will be available for inspection when requested by any of the regulatory bodies charged with the safety of human subjects and the integrity of data including, but not limited to, the oversight (Office of Human Research Ethics (OHRE) Biomedical IRB, the Oncology Protocol Review Committee (PRC) or the North Carolina TraCS Institute Data and Safety Monitoring Board (DSMB).

The UNC LCCC Data and Safety Monitoring Committee (DSMC) will review the study on a regular (quarterly to annually) basis, with the frequency of review based on risk and complexity as determined by the UNC Protocol Review Committee. The UNC PI will be responsible for submitting the following information for review: 1) safety and accrual data including the number of patients treated; 2) significant developments reported in the literature that may affect the safety of participants or the ethics of the study; 3) preliminary response data; and 4) summaries of team meetings that have occurred since the last report. Findings of the DSMC review will be disseminated by memo to the UNC PI, PRC, and the UNC IRB and DSMB.

### **8.0 STATISTICAL CONSIDERATIONS**

#### **8.1 Study Design/Study Endpoints**

This study is designed to explore associations between various parameters from FDG PET and C11-AMT PET imaging at baseline (SUVmax, k1-4 rate constants as assessed using the 3-compartmental model, total tumor metabolic volume, measurement of intra-tumoral and inter-lesion heterogeneity) and antitumor response to pembrolizumab at week 12 (or earlier, if patient progresses) that will be assessed using CT scan of the chest, abdomen and pelvis (add neck, if applicable) with IV contrast and defined via RECIST v1.1. Evaluable patients will be defined as those subjects who have successfully completed baseline FDG PET, C11-AMT PET and CT scan of the chest, abdomen, and pelvis (add neck, if

applicable) with IV contrast, have received at least 2 pembrolizumab infusions every 3 weeks (if progressed earlier than 12 weeks), and have had restaging CT scans with IV contrast to document response, disease stability, of tumor progression.

For quantitation of expression of various proteins or immune cell subsets in representative tissue sections from archived tumor blocks by immunohistochemistry or immunofluorescence, we will use the H-score, as previously described.

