In accordance with our above stated hypothesis, we plan to conduct a phase II trial of pembrolizumab administered at the FDA-approved 200mg flat dose intravenously every 3 weeks in 27 patients (23 evaluable) with systemic treatment-naïve metastatic melanoma. In addition to standard staging with whole body CT scans with IV contrast at baseline and whole body F-labelled fluorodeoxyglucose (FDG)-PET, we will also perform co-registered PET/non-contrast CT imaging using C11-AMT PET tracer and will obtain tumor tissue biopsies prior to initiation of pembrolizumab treatment. Antitumor response at 12 weeks (or earlier, if patient progresses), which will be measured by RECIST 1.1 criteria, will be correlated with various C11-AMT PET and/or FDG PET parameters (e.g. standard uptake value, K-value, total tumor metabolic volume, measurement of intra-tumoral and inter-lesional heterogeneity). We postulate that there is an intensity threshold for C11-AMT PET parameters that will correlate with response to pembrolizumab; very low C11-AMT PET activity is expected to be associated with lack of response to pembrolizumab, intermediate C11-AMT PET activity is expected to be associated with partial or complete response, whereas extremely high C11-AMT PET activity may be associated with disease stability because high IDO expression and tryptophan depletion is an important immunosuppressive mechanism. In the latter case, combination treatment with pembrolizumab and IDO inhibitors may be required to achieve an antitumor response.

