## 2.4 Secondary Endpoints

- 2.4.1 Assessment of PFS, defined as D1 of treatment until progression or death from any cause in patients with metastatic melanoma treated with pembrolizumab as front-line therapy.
- 2.4.2 Correlate tumor lesions imaged at baseline by C11-AMT PET with whole body CT scan with IV contrast (CTIVC).
- 2.4.3 Correlate tumor lesions imaged at baseline by C11-AMT PET with whole body F-FDG PET at baseline and at 12 weeks (or earlier, if patient progresses).
- 2.4.4 Perform immune score, IHC, and/or immunofluorescence to detect underlying host-immune response, expression of components of the IDO pathway (LAT1, IDO, TPH1), lymphocyte subtypes (CD4, CD8, FoxP3, MDSC), PD-1/PD-L1, and other immune checkpoint pathways (LAG3, GITR, TIM3) in freshly collected and archived tumor specimens from patients who will receive pembrolizumab. Correlate immune score and other IHC with SUVmax of the previously imaged lesion by C11-AMT PET.

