**B.** If whole body CT scan with IV contrast has been previously performed, time elapsed between the pre-study “diagnostic” CT scan with IV contrast and treatment initiation with pembrolizumab should be at most 28 days. In this case, a whole body PET scan must be performed within 28 days prior to C11-AMT PET imaging.

**C.** If both whole body PET scan and a CT scan with IV contrast (chest, abdomen, pelvis and neck if applicable) have been performed separately prior to study entry, this is acceptable as long as the whole body PET scan is within 28 days of C11-AMT PET imaging and the CT with IV contrast is within 28 days of starting pembrolizumab.

Following pembrolizumab infusions administered every 3 weeks x 4 cycles, antitumor response will be assessed at 12 weeks by performing a whole body FDG PET scan coregistered with CTIVC. As an alternative, CTIVC of the chest, abdomen, and pelvis (add neck, if applicable) is acceptable and can be used for this assessment of antitumor response by RECIST v1.1 criteria. It is quite possible that patients may progress earlier than 12 weeks; in this case, an evaluable patient will be a patient who has received at least two pembrolizumab infusions and subsequently had restaging scans to document radiographic progression and measurement by RECIST v1.1 criteria. Antitumor response will then be correlated with various C11-AMT PET parameters at baseline (e.g. SUVmax, total tumor metabolic volume, measurement of intra-tumoral and inter-lesion heterogeneity), which is the primary endpoint of the study. Toxicity will be assessed during treatment via NCI CTCAE v4.03. Following week 12, subjects will have completed study treatment requirements, and after discussion with their doctor they will be allowed to continue pembrolizumab per standard of care until disease progression or other reasons (e.g., unacceptable toxicity). Long-term follow up and treatment of all patients who continue to have clinical benefit from pembrolizumab (complete response, partial response, stable disease) will be maintained as per standard of care.

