#### 4.5 Duration of Therapy

Treatment may continue until one of the following occurs:

- Disease progression  
*Note:* For unconfirmed radiographic disease progression, please see Section 6.7
- Inter-current illness that prevents further administration of treatment
- Unacceptable adverse event(s)
- Pregnancy
- Patient decides to withdraw from study treatment, **OR**
- General or specific changes in the patient's condition render the patient unacceptable for further treatment in the judgment of the investigator

Pembrolizumab is an FDA-approved therapy for metastatic melanoma. In addition, the primary endpoint of the study is correlation between baseline AMT PET parameters and antitumor response by RECIST criteria at 12 weeks. Secondary endpoint is correlation of AMT PET parameters with PFS. It is anticipated that a considerable number of patients will have durable responses to therapy. To balance between study endpoints, sufficient follow up time, and resources patients who have had clinical benefit (complete response, partial response, stable disease) and can receive pembrolizumab per standard of care (not as part of protocol treatment).

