## **6.7 Assessment of Efficacy**

Subjects who have completed C11-AMT PET, FDG PET and CT scan of the neck, chest, abdomen, and pelvis and have received at least 2 doses of pembrolizumab will be evaluable for assessment of response and progression. Subjects whose cancer growth is documented by physical examination without imaging confirmation will count as progression. Patients who end study therapy for any reason (e.g., toxicity of treatment, decide to withdraw) will still be followed for PFS and OS.

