## 8.2 Sample Size and Accrual

A total of 27 patients will undergo C11-AMT PET imaging prior to treatment with pembrolizumab as part of the trial. Of these subjects, we anticipate <5% dropout rate, due to intolerance (pembrolizumab has a safe toxicity profile) or rapid tumor progression. Therefore, we anticipate that the total number of evaluable subjects will be 23.

Based on early clinical trials of patients who received pembrolizumab in the front line setting, the overall response rate (the sum of complete or partial response) is 45% [47, 52]. Therefore, we anticipate that 10/23 patients will respond to treatment. To test the null hypothesis that C11-AMT PET SUVmax is not correlated with response to pembrolizumab in the front line setting, we will compare the means of C11-AMT PET between responders and non-responders. With 10 responders and 13 non-responders we will have 80% power to reject the null hypothesis if the effect size is 1.1. One-sided 0.05 level test will be used.

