## 8.3 Data Analysis Plans

Apart from comparing the means of baseline FDG PET and C11-AMT PET SUVmax in responders and non-responders we will fit logistic a regression model with responder status as outcome and AMT PET SUVmax as a covariate. We will also model time-to-progression as a function of C11-AMT PET using Cox model. These analysis will be repeated with k3 as an outcome.

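### Evaluability rules remove treated patients already known to have failed from the response analysis, and section 8.3 models an undefined time-to-progression instead of the defined PFS

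*Combined protocol and SAP*

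**What the plan says.** Three sections define who is evaluable for response.

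- Section 8.1 requires baseline FDG PET, C11-AMT PET and contrast CT. Patients must also "have received at least 2 pembrolizumab infusions every 3 weeks (if progressed earlier than 12 weeks), and have had restaging CT scans".
- Section 4.2 says of those who progress before week 12 that "an evaluable patient will be a patient who has received at least two pembrolizumab infusions and subsequently had restaging scans to document radiographic progression".
- Section 6.7 requires the baseline scans and at least two doses but names no restaging CT. It adds: "Subjects whose cancer growth is documented by physical examination without imaging confirmation will count as progression". It also continues follow-up for PFS and OS in patients who stop therapy early.

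On losses, section 8.2 states "we anticipate <5% dropout rate, due to intolerance (pembrolizumab has a safe toxicity profile) or rapid tumor progression". It plans 27 imaged patients and 23 evaluable, with 10 responders and 13 non-responders.

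On time to event, section 2.4.1 reads "Assessment of PFS, defined as D1 of treatment until progression or death from any cause", and section 4.5 states "Secondary endpoint is correlation of AMT PET parameters with PFS". The analysis in section 8.3 is: "We will also model time-to-progression as a function of C11-AMT PET using Cox model". It defines no event, no handling of deaths, no censoring rule and no analysis set.

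No section counts treated but non-evaluable patients as non-responders, and none plans an all-treated or sensitivity analysis.

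**The concern.** The response endpoint is CR or PR at 12 weeks. A treated patient who has died, or has documented progression, before restaging is a known non-responder, not a missing observation. Sections 4.2 and 8.1 exclude such a patient unless two infusions and a restaging scan were achieved, and section 8.2 books rapid progression as dropout. The analysis set is thus selected partly on the outcome it is meant to measure.

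Two results are exposed. The reported ORR is biased upward, because only failures are removed by this route. The primary SUVmax comparison loses part of its non-responder group, and these are the failures a predictive marker most needs to identify. The direction of that second bias is unknown. Section 1.1 expects very low uptake to go with no response, but also says "extremely high C11-AMT PET activity may be associated with disease stability", so high uptake can sit among non-responders too.

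The sections also disagree on membership. A patient with two doses and progression on examination only is in under section 6.7 and out under sections 4.2 and 8.1.

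Finally, time-to-progression usually censors deaths without progression, whereas PFS counts them as events. In a sample of about 23 to 27, a few deaths handled either way could change the Cox result.

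**Working it through.** **Inputs.** From section 8.2: 27 imaged, 23 evaluable, 10 responders against 13 non-responders, effect size 1.1 (read as SD units), one-sided 0.05, 80% power, dropout under 5%. The documents give no SUVmax distribution.

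**1. The plan's own figure.** For a two-sample t test, df = 10 + 13 − 2 = 21 and the noncentrality is 1.1 × √(10 × 13 / 23) = 2.62. One-sided power is 81.2%, so the stated 80% reproduces. The power figure is not at fault.

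**2. How many patients could be affected.** At the stated dropout ceiling, 5% × 27 = 1.35, or about one patient. The gap between imaged and evaluable is 27 − 23 = 4. These do not agree (4/27 = 14.8%), which is a separate matter. Here they serve as the lower and upper ends of a range.

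**3. ORR.** With k early failures restored as non-responders, ORR = 10/(23 + k), with exact (Clopper-Pearson) intervals:

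| k | ORR | 95% CI |
|---|---|---|
| 0 (as planned) | 10/23 = 43.5% | 23.2 to 65.5 |
| 1 | 10/24 = 41.7% | 22.1 to 63.4 |
| 2 | 10/25 = 40.0% | 21.1 to 61.3 |
| 4 | 10/27 = 37.0% | 19.4 to 57.6 |

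The shift is 1.8 points for one patient and 6.4 points for four.

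**4. SUVmax comparison.** Suppose the evaluable patients show the planned gap of 1.1 SD, and the k excluded non-responders have a mean that differs by δ SD from the other 13. The gap with everyone included is 1.1 − kδ/(13 + k). The range δ = −1 to +1 is an assumption.

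- k = 1: 1.1 + 1/14 = 1.17 (δ = −1), to 1.1 − 1/14 = 1.03 (δ = +1).
- k = 4: 1.1 + 4/17 = 1.34 (δ = −1), to 1.1 − 4/17 = 0.87 (δ = +1).

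Adding a shifted subgroup also widens the non-responder variance, to 1 + 13kδ²/(13 + k)². After re-standardising by the pooled SD, the effect is 1.15 to 1.01 for k = 1 (power 85% to 76%) and 1.26 to 0.82 for k = 4 (power 93% to 64%). Whether the effect rises or falls depends only on the sign of δ, which is unknown.

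**5. Membership by section.**

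| Treated patient | 6.7 | 4.2 and 8.1 |
|---|---|---|
| Dies or progresses after one dose | out | out |
| Two doses, progression on examination only, no restaging scan | in | out |
| Two doses, dies before restaging | in | out |
| Two doses, early progression on restaging CT | in | in |

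The two-dose condition is in all three sections. The restaging-scan condition is only in 4.2 and 8.1. Section 6.7 does not say whether its sentence on physical examination overrides its own two-dose condition.

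**6. Time to event.** Section 2.2.2 makes PFS an objective, 2.4.1 defines it with death as an event, and 4.5 ties it to the AMT PET parameters. Section 8.3 names a different quantity and plans no PFS analysis. The footnotes to the Time and Events table (6.1) and section 6.4 collect both progression date and survival status, so PFS can be computed.

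**The case against.** The strongest reply is that the effect is small. Dosing is every three weeks, so the two-dose rule alone catches only failures in about the first three weeks, and section 6.7.6 allows treatment beyond RECIST progression, so some early progressors will still reach dose two and a scan. At the plan's dropout rate, which also covers intolerance, at most about one patient is affected: 1.8 points of ORR inside an interval about 42 points wide. This stands, with one reservation: the restaging requirement extends the exclusion to deaths and examination-only progression up to week 12. It also stands that the four-patient case goes beyond what the plan says, since some losses may be failed scans.

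Second, a minimum-exposure set is a defensible choice for asking whether a tracer predicts response to a drug, and the primary aim is exploratory. For the SUVmax comparison this has some force, and is a reason to keep that set as a sensitivity analysis. It does not justify discarding known failures from ORR. Nor does the exploratory label settle the matter, because section 8.2 specifies a formal one-sided 0.05 test with stated power.

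Third, time-to-progression may simply be loose wording for PFS, the only time-to-event endpoint defined. That is plausible, but the text does not say so, and the missing censoring rule remains under either reading.

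**Conclusion.** The concern holds and should be fixed. As written, sections 4.2 and 8.1 select the response set partly on outcome, section 6.7 conflicts with them, and section 8.3 does not analyse the defined PFS endpoint.

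The ORR bias is upward: about 2 points if one treated early failure is excluded, roughly the plan's own dropout ceiling, and at most 6.4 points if all four non-evaluable patients are treated early failures. Both figures assume 10 responders. The effect on the SUVmax comparison is a possible sensitivity, not a demonstrated bias. Within ±1 SD (assumed), the planned 1.1 SD gap becomes 1.17 to 1.03 with one excluded patient and 1.34 to 0.87 with four. No gain in power is claimed. Confidence is high on the textual conflicts; the effect on results is likely modest.

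**What to change.** - **Analysis set.** For ORR and the responder comparison, include every patient with an analysable baseline C11-AMT PET and at least one pembrolizumab dose.
- **Known failures.** Count death or documented progression, radiographic or clinical, before restaging as non-response.
- **Unknown response.** Count patients with no week-12 CT for other reasons, such as toxicity, as non-responders for ORR. Run the SUVmax comparison with and without them.
- **Sensitivity.** Keep the two-dose, restaged set as a sensitivity analysis.
- **Consistency.** Reconcile sections 4.2, 6.7 and 8.1 on progression without imaging, and stop describing rapid progression as dropout in section 8.2.
- **Time to event.** In section 8.3, replace time-to-progression with PFS as defined in 2.4.1, from Day 1, in all treated patients with a baseline C11-AMT PET, and state the censoring rule.

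The cost is wording in sections 4.2, 6.7, 8.1, 8.2 and 8.3 and one additional set of sensitivity analyses. No new data are needed, because all patients are to be imaged before treatment and section 6.7 already follows early stoppers for PFS and OS. The reported ORR will be slightly lower, by about 2 points at the plan's own dropout rate.
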